	Pretreatment EOS	
Main Inclusion Criteria	SYN-010 42 mg q.d. (n=50) SYN-010 21 mg q.d. (n=50) Placebo q.d. (n=50) Placebo q.d. (n=50) Placebo q.d. (n=50) Placebo q.d. (n=50) Clinic Visits Breath gases Cytokines in plasma Stool samples for microbiome 1. Male or female participants aged between 18 and 65 years	
	inclusive.	
	1	

2.	Patient must be willing and able to participate in the study for the required duration, understand and sign the informed consent form (ICF), and be willing to comply with all protocol-
3.	related visits and procedures. Patient has had IBS-C symptoms (as defined by Rome IV
4.	Patient has an average score of \geq 3.0 for daily abdominal pain at its worst (11-point numerical rating scale [NRS]) during and up to the 17 days immediately before randomization (i.e. Pre- treatment Period).
5.	Patient has an average of \leq 3 CSBMs per week or \leq 5 SBMs per week during the 17 days immediately before randomization (i.e. Pre-treatment Period)
6.	Patient has a breath methane level \geq 10 ppm on a lactulose breath test administered at Screening.
7.	Patient may be on a stable, continuous regimen of fiber or probiotics one month before the Screening Visit; however, they must maintain a stable dose regimen through Week 12.
8.	Patient must agree to refrain from starting a new diet, changing stable dose of supplemental fiber, or changing exercise pattern that may affect IBS-C symptoms from the time
	of Screening through the end of the study. If the patient takes food products that are strong inhibitors of cytochrome P450 3A (CYP3A) (e.g. grapefruit juice, Seville orange juice, St. John's Wort), he/she must agree to refrain from taking these from the time of Screening through the end of the study.
9.	Patient must agree to use an acceptable method of contraception from the time of signing the ICF to 30 days after the final dose of study drug if the patient is a sexually active female of child-bearing potential (defined as any female who has experienced menarche and who is NOT permanently sterile or postmenonausal. Postmenonausal is defined as 12
	consecutive months with no menses without an alternative medical cause). Adequate contraceptive measures include: oral contraceptives (stable use for two or more cycles before Screening); intrauterine device; Depo-Provera [®] ; Norplant [®]
	System implants; partner with a vasectomy; double-barrier birth control (e.g. use of a condom plus diaphragm or condom plus either contraceptive sponge, foam, or jelly); or abstinence. According to drug research standards, male patient must agree to use an acceptable method of contraception and refrain from
	donating sperm from the time of signing the ICF to 90 days after the final dose of study drug.

	10. A female patient of child-bearing potential must be non-
	pregnant and non-lactating and have negative pregnancy tests
	at the Screening Visit and on Day 1 prior to dosing with study
	drug.
	11. Patients must be able to understand and be willing to sign the
	written informed consent form. A signed informed consent
	form must be appropriately obtained prior to the conduct of
	form must be appropriately obtained prior to the conduct of
	any trial-specific procedure.
	12. Willing and able to comply with the protocol, including follow-
	up visits and examinations.
Main Exclusion Criteria	1. Patient has loose (mushy) or watery stools for > 25% of their
	bowel movements (BMs) during the 12 weeks before Screening
	or during the Screening and Pre-treatment Periods.
	2 Patient has a history of cathartic colon laxative or enema
	abuse.
	3. Patient has a history of ischemic colitis.
	4 Patient has a history of pelvic floor dysfunction.
	5 Patient has a history of bariatric surgery for the treatment of
	obesity.
	6. Patient has a history of surgery to remove a segment of the
	gastrointestinal (GI) tract at any time before the Screening
	Visit.
	7. Patient has any history of myopathy, rhabdomyolysis, chronic
	myalgia, or familial history of hereditary muscular disorders.
	8. Patient has been diagnosed with or has a family history of
	familial adenomatous polyposis, hereditary nonpolyposis
	colorectal cancer, or any other form of familial colorectal
	cancer.
	9. Patient currently has any structural abnormality of the GI tract
	or a disease or condition that can affect GI motility, or any
	unexplained and clinically significant symptoms such as lower
	GI bleeding, rectal bleeding, heme-positive stool, iron-
	deficiency anemia, weight loss, or systemic signs of infection.
	10. Patient has had any previous surgery involving the abdomen.
	pelvis, or retroperitoneal region during the last 12 months
	prior to Screening, with the exclusion of laparoscopic
	gallbladder surgery or appendix removal.
	11. Patient has a history of diverticulitis or any chronic condition
	that could be associated with abdominal pain or discomfort
	and could confound the assessments in the study (e.g.
	inflammatory bowel disease chronic nancreatitis nolycystic
	kidney disease, ovarian cysts, endometriosis, or lactose
	intolerance)
	intereruncej.

 Patient has history of severe renal insufficiency defined as an actual or estimated glomerular filtration rate of < 30 mL/min/1.73 m² within the 6 months prior to Screening Visit. Patient has any history of a medical condition or a concomitant
medical condition that, in the opinion of the investigator, would compromise the patient's ability to complete the study safely or could confound the assessments in this study (e.g. uncontrolled hypothyroidism).
14. Patient is known to have elevated liver enzyme levels (aspartate aminotransferase [AST], alanine aminotransferase
[ALT], alkaline phosphatase [ALP]) or creatine kinase levels that are \geq 1.5 times the upper limit of normal (ULN) that have not been resolved within the 4 weeks prior to consent and/or these elevated levels are present at the Screening Visit
laboratory assessment
 Patient has any abnormal laboratory results, electrocardiogram (ECG) findings, or physical examination findings deemed clinically significant by the investigator during the Screening Period.
16. Within 14 days prior to the Screening Visit, patient has used concomitant medications that are: (1) moderate-to-strong inhibitors of cytochrome P450 3A (CYP3A) and/or organ anion transporting polypeptide (OATP)1B1 (e.g. cyclosporine, verapamil, dronedarone, diltiazem, amiodarone, itraconazole,
ketoconazole, posaconazole, voriconazole, clarithromycin, telithromycin, human immunodeficiency virus protease inhibitors, boceprevir, telaprevir, nefazodone, erythromycin, cobicistat-containing products); (2) other concomitant
medications that are excluded from the lovastatin label (e.g. rifampin, colchicine, ranolazine); or (3) metformin or GLP-1 agonists. Patients should not take any of these concomitant medications during the treatment phase of the study without contacting the investigator.
 17. Patient has hypersensitivity to statins; or has used any statins, fibrates, > 1 g/day of niacin, or gemfibrozil within the 3 months prior to the Screening Visit.
18. Patient reports current chronic or frequent use of drugs known to cause constipation (e.g. narcotics) for the 3 months prior to Screening.
19. Patient has taken over-the-counter IBS treatments (e.g. laxatives) or proton pump inhibitors within 3 days prior to the Screening Visit.
20. Certain drugs used for the treatment of IBS (e.g. low dose
tricyclic antidepressants) may be allowed at the discretion of
the Medical Monitor provided the patient remains on a stable
the study with the exception of tegaserod, lubiprostone.

	 linaclotide, metoclopramide, prucalopride, domperidone, plecanatide, CandiBactin, Atrantil, Allimax/Allimed within 2 weeks prior to the Screening Visit or antibiotics within 2 months prior to the Screening Visit. 21. Patient has used an opioid chronically or frequently within the 3 months prior to the Screening Visit and for the duration of the study. 22. Patient is currently enrolled in, or plans to enroll in, another clinical study or has used any investigational drug or device within 1 month before signing the ICF through the completion of the study. 23. Patient has previously participated in a SYN-010 study. 24. Patient has a history of alcohol or drug abuse within the 12 months prior to the Screening Visit.
Inclusion	provided an ID number and password-protected access to the REDCap website to record Baseline parameters (such as weekly average worst abdominal pain score and weekly number of CSBMs). During this
	period, patients will also (i) complete a lactulose breath test including analysis of methane, hydrogen, hydrogen sulfide and carbon dioxide; (ii) provide a stool sample for analysis of the microbiome; and (iii) provide a blood sample for analysis of cytokines. Patients will be eligible for randomization if they have a breath methane level of \geq 10 ppm on the lactulose breath test and fully respond to the PRO questionnaires in the REDCap system on at least 11 of 14 days of the Screening and Pre-treatment Period. On Day 1, eligible patients will be randomized in a 1:1:1 ratio to receive study drug (SYN 010 21 mg, SYN-010 42 mg, or placebo). Study drug will be administered during the Treatment Period once daily at bedtime for up to 12 weeks. Rescue medication, bisacodyl, magnesium citrate, magnesium hydroxide, or lactulose, will be allowed for severe constipation (i.e. when symptoms become intolerable). Dosage and frequency should be followed according to package insert. For the Randomization Visit only, rescue medication will not be allowed on the day before, the day of, or the calendar day after the Randomization Visit. Patients will be asked to refrain from starting a new diet, changing stable dose of supplemental fiber and/or changing their exercise patterns that may affect IBS-C symptoms from the time of Screening throughout the duration of the study. Patients will also be asked to refrain from taking food products that are strong inhibitors of cytochrome P450 3A (CYP3A) (e.g. grapefruit juice, Seville orange juice, St. John's Wort), from the time of Screening throughout the duration of the study.

Adjustment and			
Management			
Criteria for Evaluation Three analysis populations are defined for this study. The	Three analysis populations are defined for this study. The Intent to		
Study Endpoints Treat (ITT) patient population will consist of all patients	who are		
randomized. The full analysis set will consist of all randomize	d patients		
who receive at least 1 dose of study drug. The full analysis	et will be		
used for the efficacy and safety analyses. Efficacy analys	is will be		
conducted according to the randomized treatment the	patients		
receive, and safety analysis will be conducted according to	the actual		
treatment the patients receive.			
The per-protocol set will consist of all patients in the full a	nalysis set		
who do not have major protocol deviations as specified in the	statistical		
analysis plan.			
Plan for Statistical Analysis Efficacy:			
The analysis for the change from baseline in weekly number	of CSBMs		
will be performed using the analysis of covariance (ANCC	OVA) with		
treatment group and the Baseline value as covariates usir	g the ITT		
analysis set. The primary analysis will be conducted using the	observed		
values. For missing data, two sensitivity analyses will be con	ducted by		
using the multiple imputation and last observation carrie	forward		
(LOCF) methods. Details will be included in the statistical an	alysis plan		
(SAP).	, ,		
For secondary and exploratory analyses, the Chi-squared te	est will be		
used to determine differences between treatment g	oups for		
categorical variables. For continuous-type variables, an	nalysis of		
covariance (ANCOVA) methods will be used with treatment a	group and		
the corresponding baseline value as covariates. For the	esponder		
endpoints, the analysis will be conducted by imputing the mi	ssing data		
as "non-responders". A sensitivity analysis will be conc	ucted by		
imputing the missing data as "responders". All statistical te	sts will be		
conducted at a 2-sided significance level of 5% unless	otherwise		
specified.			
Due to the COVID-19 pandemic, study enrollm	ent was		
temporarily stopped, at which time 53 patients h	ad been		
randomized to study drug treatment groups. A futilit	y interim		
analysis will be conducted on these 53 patients (49 have		
completed the study and 4 have withdrawn/early ter	ninated).		
Safety:			
All AEs will be analyzed in terms of descriptive statistics and o	ualitative		
analysis. Adverse events will be listed for each patient and su	mmarized		
by system organ class (SOC) and preferred term (PT) using the	e Medical		
Dictionary for Regulatory Activities (MedDRA). Safety labora	tory data		
ECGs, physical examination findings and vital signs measured	nents will		
be listed for each patient and presented descriptively by	reatment		
group time points.			

Sample Size Rationale	A total of 150 adult IBS-C patients: 50 in the placebo group and 50 in
	each of the SYN-010 21 mg and SYN-010 42 mg treatment groups. The
	sample size calculation is based on the following assumptions: the
	weekly CSBM change from baseline is 0.5 for the placebo group, and
	1.5 for each active group, with common standard deviation of 1.5, the
	study will have 90% power for each SYN-010 group compared with the
	placebo by using the t-test with alpha=0.05.

2. General information

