Due to the COVID-19 pandemic, study enrollment was temporarily stopped, at which time a total of 53 patients had been randomized to study drug treatment groups. 49 of these patients have completed the study and 4 have withdrawn or early terminated. A futility interim analysis will be conducted based on the data from these 53 patients. A recommendation to stop enrollment of the study will be made by the unblinded statistician(s) if, for both dose groups, the conditional power is less than 20% based on the primary endpoint AND the difference of the overall 12-week responder rates is less than 2%. The interim analysis will be conducted by a group of people that are not involved in the daily activities of the study. Details will be included in the SAP.

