6.8 Determination of sample size

The sample size calculation is based on the following assumptions: the weekly CSBM change from baseline is 0.5 for the placebo group, and 1.5 for each active group, with common standard deviation of 1.5; 50 patients in each group will have 90% power for each SYN-010 group compared with the placebo by using the t-test with alpha=0.05.

7. Study population

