# 2.2. DETERMINATION OF SAMPLE SIZE

The sample size calculation is based on the following assumptions: the weekly CSBM change from baseline is 0.5 for the placebo group, and 1.5 for each active group, with common standard deviation of 1.5. Fifty subjects in each group will have 90% power for each SYN-010 group compared with the placebo by using the t-test with 2-sided alpha = 0.05.

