# 2.3. RANDOMIZATION AND ADMINISTRATION OF STUDY DRUG

After successful completion of the Screening and Pre-treatment Period, eligible patients will be randomized in a 1:1:1 ratio to receive study drug (SYN-010 21 mg, SYN-010 42 mg, or placebo). Subjects will take SYN-010 or matching placebo orally once daily at bedtime for 12 weeks.

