#### **6.4.** MISSING DATA

For the analyses of various weekly responses, the week with missing assessments for more than 3 days will be treated as "non-responder" for the week. If a subject drops out of the study or otherwise does not report efficacy data for a particular treatment-period week, the subject will not be considered a responder for that week.

For the analyses of various weekly average scores for IBS symptoms, the weekly average score will be set to "missing" if there are more than 3 days with missing assessments during a week, and the data will be considered as "missing" for the week. An observed-cases approach to missing data will be applied to the continuous type variables; this means that if the data is considered as "missing" for the week, the average of the non-missing data over the 12 weeks of the treatment period will be the subject's value for that week.

Subjects will be assumed to have not had bowel movement nor taken rescue medication if the corresponding daily question is not answered.

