#### 8.1. PRIMARY EFFICACY ENDPOINT AND ANALYSIS

The primary endpoint is the change from baseline in the weekly average number of CSBMs during the 12-week treatment period.

The analysis for the primary endpoint will be performed using the analysis of covariance (ANCOVA) with treatment group and the baseline value as covariates based on the full analysis set. The primary analysis will be conducted using the observed values. To control the overall false positive rate at 0.05, the Hochberg testing procedure will be used. Specifically, let  $P_1$  and  $P_2$  be the P-values from the ANCOVA comparing the 42 and 21 mg dose group with the placebo, respectively, if  $Max(P_1,P_2) \leq 0.05$ , then the primary endpoint will achieve statistical significant for both doses. Otherwise, if  $Min(P_1,P_2) \leq 0.025$ , then the primary endpoint will achieve statistical significance for the dose that has smaller P-value. If  $Min(P_1,P_2) > 0.025$ , then the primary endpoint will not achieve statistical significance for either dose group. The nominal P-values and 95% confidence intervals (CI) will be provided from the ANCOVA model.

Two sensitivity analyses will be conducted by using the multiple imputation and last observation carried forward (LOCF) methods to impute the missing data for the primary endpoint. The same ANCOVA model will be used for the sensitivity analyses.

In addition, the analyses of the primary endpoint will be performed based on the PP population using the same statistical model.

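### The SAP's own-average rule leaves multiple imputation and LOCF almost nothing to impute for the primary endpoint, and no planned analysis of that endpoint expressly tests loss of benefit after stopping

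*Protocol*

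**What the plan says.** The primary endpoint is the change from baseline in weekly average CSBMs over the 12-week treatment period. It is analysed by ANCOVA on observed values (protocol 6.6, SAP 8.1).

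- **Sensitivity analyses.** The protocol synopsis and section 6.6 name two, "using the multiple imputation and last observation" carried forward, and leave the details to the SAP. SAP 8.1 repeats "multiple imputation and last observation carried forward (LOCF) methods to impute the missing data for the primary endpoint" and adds only that the same ANCOVA is used. It states no imputation model, no level (week or 12-week average) and no missingness assumption.
- **Missing weeks.** SAP 6.4 sets a weekly average to missing when more than 3 days are unassessed. For continuous variables it then says that "the average of the non-missing data over the 12 weeks of the treatment period will be the subject's value for that week".
- **Missing days.** The last sentence of SAP 6.4 treats an unanswered daily question as no bowel movement and no rescue medication. The CSBM formula in SAP 8.2.1 instead divides by the number of days with a CSBM assessment.
- **Dropout so far.** Protocol 6.6 reports that "49 of these patients have completed the study and 4 have withdrawn or early terminated", out of 53 randomized. No planned dropout rate is given.

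**The concern.** A sensitivity analysis for missing data should vary the assumption made about the unobserved weeks. Here the assumption most open to challenge is that a patient who stops early would have kept the response seen before stopping. The own-average rule builds that assumption into the primary value: a patient who leaves after Week 3 is scored for 12 weeks on Weeks 1 to 3. If the two sensitivity analyses run after that rule, they reproduce the primary result for everyone with a valid week. If they run on weekly data, they still extend what was seen on study. Agreement among the three could then be reported as robustness to dropout when loss of benefit had not been tested.

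The conflict between the SAP 6.4 rules matters as well, because it decides whether a dropout keeps the earlier response or is scored at zero CSBMs. A borderline result has consequences beyond the primary endpoint, since SAP 8.2.1 opens formal secondary testing only if both doses are significant.

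**Working it through.** **1. Inputs from the documents.** Difference 1.5 − 0.5 = 1.0 CSBM/week, "for each active group, with common standard deviation of 1.5" (SAP 2.2); 50 per group (protocol 6.8); "eligible patients will be randomized in a 1:1:1 ratio" (SAP 2.3); "the t-test with 2-sided alpha = 0.05" (SAP 2.2).

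**2. The plan's own figure.** Standard error (SE) = 1.5 × √(2/50) = 0.30, so the assumed effect is 1.0/0.30 = 3.3 SE. Power from the noncentral t is 0.910 (normal approximation 0.915). The statement that "50 patients in each group will have 90% power for each SYN-010 group" reproduces.

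**3. What is left to impute.**

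| Rule applied first (SAP 6.4) | Missing for MI and LOCF |
|---|---|
| Missing week takes own average | Only patients with no valid week; LOCF has no post-baseline value to carry for them |
| Unanswered day = no bowel movement | No CSBM value is missing |
| More than 3 missing days = missing week, nothing filled | Missing weeks, so both methods have work to do |

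**4. How far the rules differ for one patient.** Assume a baseline of 1 CSBM/week and a change of 1.5 in Weeks 1 to 3 (weekly count 2.5), then dropout.
- Own average: 12-week change = 1.5.
- Unanswered days count as zero: (3 × 2.5 + 9 × 0)/12 − 1 = 0.625 − 1 = −0.375.

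**5. Size of the untested assumption.** Dropout is 4/53 = 7.5% (exact 95% CI 2.1% to 18.2%). Assumptions not in the documents: the drug effect rises linearly over 4 weeks and then stays flat; stopping falls equally often after each of Weeks 1 to 11, at the same rate in both arms and unrelated to response; the drug effect is zero after stopping.

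For a 12-week mean effect of 1.0 the plateau c satisfies c × (0.25 + 0.50 + 0.75 + 9)/12 = 1, so c = 1.143. Averaged over the 11 stopping weeks, the effect credited to a dropout is:
- own average of observed weeks: 0.763
- LOCF on weekly values: 0.874
- benefit lost after stopping: 0.437

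The trial-level difference is 1 − d × (1 − credited effect), with d the dropout rate.

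| d | Own average | LOCF | Benefit lost | Overstatement | In SE (÷ 0.30) |
|---|---|---|---|---|---|
| 7.5% | 0.982 | 0.991 | 0.958 | 0.025 to 0.033 | 0.08 to 0.11 |
| 20% (assumed) | 0.953 | 0.975 | 0.887 | 0.065 to 0.087 | 0.22 to 0.29 |

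A simulation of 3,000 trials with the same set-up gave 0.985, 0.994 and 0.960 at 7.5%, and 0.957, 0.979 and 0.894 at 20%, in agreement. A MAR imputation by arm and week would restore about 1.00, an overstatement of 0.04 at 7.5%.

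**6. Patients who worsen before leaving.** Keep the same set-up, but let the effect be lost already in the last observed week. The credited effects become 0.562 (own average), 0.355 (LOCF) and 0.355 (benefit lost). At 20% dropout the differences are 0.912, 0.871 and 0.871. LOCF now lies below the primary and equals the lost-benefit value.

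**The case against.** A reader might infer that neither sensitivity analysis can ever challenge the primary result, or that all three analyses assume lasting benefit. The documents do not support that.

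- LOCF carries the last observed week, good or bad, in every arm. Step 6 shows it falling below the primary when patients worsen before leaving. This stands.
- If the rule on unanswered questions governs the days after dropout, the primary analysis already scores dropouts at zero CSBMs. It then penalises them and preserves nothing. This stands too, and it is why the conflict in SAP 6.4 belongs to the point.
- No document says that the multiple imputation is of the MAR kind. An unspecified imputation could still be made reference-based. The fair criticism is that it is unspecified.
- The more-than-3-days rule does create missing weeks, so having nothing to impute depends on which rule is applied first.
- At the reported dropout the effect is small, and the assumed 20% lies just above the upper confidence limit of 18.2%.
- The CSBM-based stool-frequency responder endpoint counts missing weeks as non-response, so dropout is penalised on a related measure. That endpoint is secondary, however, and is not a sensitivity analysis of the primary.

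None of this supplies an analysis of the primary endpoint that expressly tests loss of benefit after stopping.

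**Conclusion.** The point holds in limited form. Under the own-average rule, multiple imputation and LOCF have almost nothing to impute at the 12-week-average level. On weekly values, LOCF and a MAR imputation extend on-study data, and loss of benefit after stopping is not expressly tested. Whether a dropout is credited or penalised depends on which SAP 6.4 rule applies, and the SAP does not say.

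The size is about 0.03 CSBM/week, or 0.1 SE, at 7.5% dropout, and about 0.07 to 0.09 at an assumed 20%. These figures rest on the assumed four-week build-up, stopping unrelated to response, equal dropout in both arms and complete loss of effect after stopping. At the dropout seen so far, the shift would matter only for a borderline result. It grows with higher or unequal dropout: with a steady effect and assumed rates of 30% on active and 15% on placebo, a separate simulation gave about 1.00 for the primary, LOCF and MAR imputation, against 0.86 with benefit lost. The gap of 0.14 is nearly half an SE. The point is a cheap improvement to what the trial can claim about robustness. It does not show that the primary result would be wrong.

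**What to change.** In SAP 6.4 and 8.1, with matching text in protocol 6.6 and the synopsis:

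1. State that a week with more than 3 missing diary days is missing for CSBMs. Limit the rule that an unanswered question means no bowel movement to days within an otherwise valid week, and say whether such a day counts in the denominator of the SAP 8.2.1 formula.
2. Run the multiple imputation on weekly CSBM values, state its model, then average over 12 weeks and apply the same ANCOVA.
3. Add one control-based (jump-to-reference) multiple imputation, in which only unobserved weeks after study drug is stopped are imputed from the placebo arm. Protocol 7.4 separates stopping study drug from leaving the study, so any off-drug diary data that were observed must be kept.

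LOCF may stay as a supportive analysis. The SAP cites Protocol Version 3.0 and the protocol supplied is Version 8.0, so the two texts should be aligned in the same revision.

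The cost is SAP wording and some programming. Randomization, visits and sample size do not change. The added sensitivity estimate will usually be slightly less favourable to the drug.
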